## **5 Risks and Benefits**

### **5.1 Potential risks**

#### **Medication:**

The potential risks associated with bupivacaine include neurologic and cardiac toxicity, if injected intravascularly. However, the risk is very low because a trained anesthesiologist using ultrasound guidance will perform the PECS II block and a trained orthopedic surgeon will be performing the skin infiltration. US guidance allows the anesthesiologist to see and avoid blood vessels when administering the medication. Additionally, the syringe of the local anesthetic will be aspirated prior to injection by the anesthesiologist and surgeon to ensure that the block needle tip is not intravascular. A PEC II block is fascial plane block and not a nerve block. The local anesthetic will be injected between the pectoralis major and serratus anterior muscle. The risk of nerve injury or intravascular injection in the PECS II is therefore similar to the surgical infiltration arm of the study. Allergic reactions to local anesthetic is possible however, any subjects with a history of allergies to local anesthetic will be excluded from the study.

#### **Procedure:**

##### Pecs II:

The potential risks associated with Pecs II include bleeding, nerve damage, pleural injury, infection at injection site, intravascular injection, and local anesthetic systemic toxicity. LAST is generally secondary to intravascular injection. The likelihood of this occurring is low due to the expertise of the anesthesiologist and use of ultrasound guidance.

##### Surgical infiltration:

The potential risks associated with surgical infiltration include bleeding, nerve damage, pleural injury, infection at injection site and local anesthetic systemic toxicity. However, the likelihood is low due to the expertise of the surgeon performing the injection, the sterile environment, and the safe practice of clinicians.

### **5.2 Potential benefits**

Study subjects may experience better pain control, improved satisfaction, decreased need for opioids and reduced incidence of side effects. If the study is not inconclusive, the study's results may benefit future patients by showcasing Pecs II block improves pain control in the first 24 hours of an Open Subpectoral Biceps Tenodesis. Additionally, advocate for the use of Pecs II block as the standard of care for peri- and postoperative pain control in future patients undergoing Open Subpectoral Biceps Tenodesis.

CONFIDENTIAL

This material is the property of the NYU School of Medicine and Langone Medical Center. Do not disclose or use except as authorized in writing by the study sponsor

## 6 Statistical Analysis

### 6.1 General Approach

The primary analysis will follow the intention-to-treat (ITT) principle in order to evaluate the true outcome of the intervention as experienced by the patient who is blinded to the intervention.

Continuous and categorical baseline characteristics will be compared using Hedges standardized difference

Normally distributed data will be compared using t tests while non-normally distributed continuous outcomes will be assessed using the Mann-Whitney U test.

It is anticipated that the data for some subjects will be incomplete for various reasons: missing daily-diary entries, refusal to answer a question on the questionnaire, onset of illness, loss-to-follow-up, etc. All occurrences of incomplete data will be investigated to carefully document the reasons for the missing data. If the primary outcome (amount of opioid utilization for the first 24 hours after surgery) cannot be ascertained with a reasonable degree of certainty, the patient will be excluded from the data analysis.

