Statistical Analysis	Continuous and categorical baseline characteristics will be compared using Hedges standardized difference. Outcomes will be assessed using an intention-to-treat (ITT) methodology. Normally distributed data will be compared using t tests while non-normally distributed continuous outcomes will be assessed using the Mann-Whitney U test.

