### **3.6 Total Number of Participants and Sites**

Recruitment will end when 160 participants have been enrolled. It is expected that there will be subjects enrolled who will be lost to follow up and be evaluated by intention-to-treat. The sites for enrollment will be the NYU Langone Orthopedic Hospital and NYU Ambulatory Surgery Center at 38th street.

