#### Secondary Endpoints:

1. Patient reported NRS scores in PACU and at 24 hours
2. Patient Reported NRS scores on POD 1 and POD 3
3. Reaction to surgical subpectoral incision (signs include patient movement, tachycardia, etc.)
4. Skin assessment of sensation in PACU (axilla, distal to surgical dressing)

Normally distributed data such as the primary outcome variable will be compared using the two-sample t-test. In the case that the data are not normally distributed, the Wilcoxon rank-sum test will be used instead. Categorical variable will be compared using the Chi-Squares unless other tests such as the Fisher's exact test are more appropriate.

All endpoints will be evaluated as fits the data set with graphical figures such as scatter plots, box-and-whisker plots, and frequency histograms to visualize the distribution of these outcomes and their relationships to covariates and treatment assignment. When appropriate descriptive graphical and tabular methods will also be estimated and presented in a graphical figure.

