### 7.4 Time Period and Frequency for Event Assessment and Follow-Up

The occurrence of an AE or SAE may come to the attention of study personnel during study visits and interviews of a study participant presenting for medical care, or upon review by a study monitor. All AEs including local and systemic reactions not meeting the criteria for SAEs will be captured on the appropriate RF. Information to be collected includes event description, time of onset, clinician's assessment of severity, relationship to study product (assessed only by those with the training and authority to make a diagnosis), and time of resolution/stabilization of the event. All AEs occurring while on study must be documented appropriately regardless of relationship. All AEs will be followed to adequate resolution.

Any medical condition that is present at the time that the participant is screened will be considered as baseline and not reported as an AE. However, if the study participant's condition deteriorates at any time during the study, it will be recorded as an AE. UPs will be recorded in the data collection system throughout the study.

Changes in the severity of an AE will be documented to allow an assessment of the duration of the event at each level of severity to be performed. AEs characterized as intermittent require documentation of onset and duration of each episode.

The PI will record all reportable events with start dates occurring any time after informed consent is obtained until 7 (for non-serious AEs) or 30 days (for SAEs) after the last day of study participation. At each study visit, the investigator will inquire about the occurrence of AE/SAEs since the last visit. Events will be followed for outcome information until resolution or stabilization.

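### Section 6.1 excludes the patient when the 24-hour opioid total is uncertain and does not limit this to the primary endpoint, so completed operating-room and PACU results would drop out of the secondary analyses

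*Combined protocol and SAP*

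**What the plan says.** Section 6.1 (General Approach) expects incomplete data and closes with an exclusion rule. The condition is that the primary outcome "cannot be ascertained with a reasonable degree of certainty"; the consequence is that "the patient will be excluded from the data analysis". No endpoint or analysis set is named, and no other section defines a separate set for secondary or side-effect data.

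Three other statements bear on the rule:

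- Section 6.1 itself: "The primary analysis will follow the intention-to-treat (ITT) principle".
- Protocol Summary, Statistical Analysis: "Outcomes will be assessed using an intention-to-treat (ITT) methodology". This covers outcomes generally.
- Section 3.6 expects that "there will be subjects enrolled who will be lost to follow up and be evaluated by intention-to-treat".

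Section 6.2 lists the secondary endpoints: NRS pain in PACU and at 24 hours, NRS on POD 1 and POD 3, reaction to the subpectoral incision, and skin sensation in PACU. Under section 2.1 the skin test is done before discharge, PACU opioid use is taken from EPIC, and home use is collected by phone on POD 1 and POD 3. The attached Medication Usage Record also logs the time and number of pills.

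**The concern.** The rule is triggered by one variable but removes the patient, not just that value. Reaction to incision is seen in the operating room, and the PACU pain score and skin test are complete before the patient leaves. The part of the opioid total most likely to be uncertain, use at home, is collected later. A patient can therefore have valid results on three secondary endpoints, and perhaps a POD 3 pain score, and still be removed from all of them.

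Whether the total can be established is known only after randomisation and may be related to outcome. Section 6.1 itself names illness and loss to follow-up among the expected reasons for missing data. Under section 4.2.4, a patient who withdraws needs no further follow-up, so someone withdrawing within 24 hours would probably meet the trigger. Yet section 10.3 allows information gathered before a patient revokes authorization to be used. Dropping these results would make the secondary comparisons less precise and open them to selection, although the data are already in hand.

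**Working it through.** **1. The plan's own sample size.** Inputs from section 6.3: means 25 and 32 mg (difference 7), common SD 13, two-sided alpha 0.05, power 0.90.

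n per group = 2 × [13 × (1.960 + 1.282) / 7]² = 72.48.

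This rounds up to 73 (74 with the exact t calculation), against 72 stated. Power at 72 per group is 0.898 (normal) or 0.894 (t). The stated figure is reproduced closely enough, and nothing here turns on the difference.

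**2. Room for exclusions.** Section 6.3 enrols 80 per arm against 72 needed and gives no dropout rate. The margin is (80 − 72)/80 = 10%. I therefore assume an excluded share f of 5% to 10%, as an illustration only.

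**3. Which endpoints need the 24-hour total?**

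| Endpoint | Where obtained | Needs the total? |
|---|---|---|
| Opioid use to 24 hours (primary) | Surgery, PACU and home | Yes |
| Reaction to incision | Operating room | No |
| NRS in PACU | PACU | No |
| Skin sensation | PACU, before discharge | No |
| NRS on POD 3 | Phone call | No |

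**4. Loss of precision if the rule is applied as written.** Patients lost per arm = 80f. Standard-error inflation = 1/√(1 − f) − 1. As a concrete case, the 95% CI half-width for a difference in proportions at an assumed 50% rate is 1.96 × √(2 × 0.25/n).

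| f | Lost per arm | n per arm | SE rise | CI half-width |
|---|---|---|---|---|
| 0 | 0 | 80 | – | 15.5 points |
| 5% | 4 | 76 | 2.6% | 15.9 points |
| 10% | 8 | 72 | 5.4% | 16.3 points |

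**5. Selection within an arm.** The shift in an arm's proportion is f × (proportion in excluded patients − proportion in retained patients). At f = 10% the largest possible value is 10 points. It requires all 8 excluded patients to share one outcome and the retained patients all to have the other, for example 8/80 = 10% becoming 0/72 = 0%. In the middle of the scale, even complete selection gives 40/80 = 50% becoming 32/72 = 44.4%, a shift of 5.6 points. These are bounds for one arm. The documents give no figure for the actual association, or for any difference between arms.

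**6. Effect of the fix on the primary endpoint.** Limiting the scope of the rule changes neither the sample size nor the primary power.

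**The case against.** The strongest reply is that the sentence is conditioned on the primary outcome, so its consequence can be read as applying to the primary analysis only. The Protocol Summary and section 3.6 both promise intention-to-treat. On that view the sentence merely lacks a scope, and the plan has not decided to discard operating-room and PACU data. Part of this stands: the documents conflict, and whole-patient exclusion is not their settled position. But section 6.1 is the specific operating rule, it sits under an approach governing all endpoints, and it refers to the primary analysis by name when it means only that. An analyst who follows it literally drops the patient everywhere. One who prefers the other reading would be choosing secondary denominators that the plan does not fix.

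Two stronger readings are tempting and should be resisted.

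- A reader might infer that missing the POD 1 call removes the patient. It does not. In-hospital use is documented by staff, home use is asked about again on POD 3, and the Medication Usage Record gives pill counts and times. The rule applies only if the total is still uncertain after all of these.
- A reader might infer that adverse events are lost. Section 7.4 requires that "All AEs occurring while on study must be documented appropriately regardless of relationship", and section 7.6 provides for periodic review; neither depends on section 6.1. Adverse events are not a listed endpoint in section 6.2. Only a between-arm comparison of the opioid side effects hypothesised in section 1.2 could be affected.

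It is also fair to say that the precision loss is small at plausible rates.

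**Conclusion.** The point holds as one of scope and consistency. As written, section 6.1 takes completed incision-reaction, PACU pain, PACU sensation and any POD 3 pain data out of the analysis on a post-randomisation criterion that those endpoints do not need. It also contradicts the intention-to-treat statements in the Protocol Summary and section 3.6.

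The effect on precision is modest: 4 to 8 patients per arm and about 2.6% to 5.4% on secondary standard errors, resting entirely on an assumed 5% to 10% exclusion rate. Selective loss matters more but cannot be sized from the documents. A reader might take the 10-point shift as an expected bias; it is a boundary extreme under an assumed rate, and nothing in the documents shows that exclusion would differ by arm. The primary endpoint's sample size and power are not in question here.

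**What to change.** Amend the last sentence of section 6.1 along these lines:

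> Uncertainty about the 24-hour opioid total affects only analyses that use that total; their handling, including in the primary analysis, is stated separately. Every randomised patient remains, by assigned arm, in the analysis of each secondary endpoint, and in any between-arm summary of opioid side effects, for which data exist. The number analysed per arm is shown for each.

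The separate statement on the primary analysis must be written, not left implied, and it must be reconciled with the Protocol Summary and section 3.6 so that all three places describe the same treatment of patients lost to follow-up.

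This costs a short edit to section 6.1 and a consistency check of the other two places. No new data are collected. The downside is that denominators will differ between endpoints and must appear in every table.

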### 6.2 Analysis of Endpoints

#### Primary Endpoints:

1. Opioid utilization for the first 24 hours after surgery, including during surgery, calculated as oxycodone equivalent.

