### CONFIDENTIAL

## Protocol Summary

Title	Pecs II Block versus Surgeon Infiltration for Open Subpectoral Biceps Tenodesis
Brief Summary	A phase IV, randomized, single-blind, single-center study measuring the effects of Pecs II block with 0.25% bupivacaine versus surgeon infiltration with 0.25% bupivacaine on postoperative pain control and opioid utilization in participants who undergo open subpectoral tenodesis.
Phase	Clinical study phase IV
Objectives	To determine if Pecs II block is superior to surgical infiltration in reduction of axillary pain after open subpectoral bicep tenodesis, especially in terms of duration.
Methodology	Phase IV, randomized, single-blind, single-center study
Endpoint	
Primary Endpoint: Opioid utilization for the first 24 hours after surgery, including during surgery, calculated as oxycodone equivalent.
 
Secondary Endpoints: Patient reported VAS scores in PACU Patient reported VAS scores on POD 1 and POD 3 Reaction to surgical subpectoral incision (signs include patient movement, tachycardia, etc.) Skin assessment of sensation in PACU (axilla, distal to surgical dressing)

Study Duration	The study will continue until 80 subjects are enrolled per arm, to allow for potential dropout and increased power.
Participant Duration	Each participant will be enrolled on DOS and complete their final follow up on postoperative day three.
Duration of IP administration	Once during surgery
Population	80 patients per study arm scheduled for open biceps tenodesis
Study Sites	NYU Langone Orthopedic Hospital and NYU Ambulatory Surgery Center at 38 th street
Number of participants	160
Description of Study Agent/Procedure	Patients in both groups will receive an interscalene nerve block with 20 mL 0.5% bupivacaine. Subjects in the Pecs II block group will receive a Pecs II fascial plane block with 20 mL 0.25% bupivacaine. The Surgical infiltration group patients will receive local infiltration of 0.25% bupivacaine by the surgeon, up to 15 mL.
Reference Therapy	Reference is Interscalene block with 0.5% bupivacaine and surgical infiltration with bupivacaine 0.25%
Key Procedures	Interscalene block with 0.5% bupivacaine, Pecs II block with 0.25% bupivacaine, local surgical infiltration with 0.25% bupivacaine

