### 1.1 Specific Aims

This study will aim to compare Pecs II block versus surgical infiltration for axillary pain in patients undergoing arthroscopic shoulder surgery with an open subpectoral bicep tenodesis.

**AIM 1:** To determine if Pecs II block is superior to surgical infiltration in reduction of axillary pain after open subpectoral bicep tenodesis, especially in terms of duration.

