### 1.3 Objectives and Purpose

The goal of this study is to compare the postoperative pain control using a Pecs II block with 0.25% bupivacaine to the standard of care of local surgeon infiltration with 0.25% bupivacaine following open subpectoral biceps tenodesis, particularly in terms of duration of pain control and adjunctive postoperative analgesic consumption. The primary objective will be to compare opioid utilization between the two arms within the first 24 hours after surgery, including intraoperatively, as measured by oxycodone equivalents. Our secondary objectives are measuring patient reported pain scores in PACU and at 24 hours, reaction to surgical incision, and skin assessment of sensation in the PACU.

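### Aim 1 concerns axillary pain and how long relief lasts, but no listed endpoint specifies a pain score at that site or a duration

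*Combined protocol and SAP*

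**What the plan says.** **Aim.** Section 1.1 has one numbered aim: superiority of the Pecs II block "in reduction of axillary pain after open subpectoral bicep tenodesis, especially in terms of duration". The Protocol Summary repeats it as the objective: "reduction of axillary pain after open subpectoral bicep tenodesis, especially in terms of duration". The goal sentence of 1.3 does not name the axilla but also stresses duration: "particularly in terms of duration of pain control and adjunctive postoperative analgesic consumption".

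**Endpoints.** The primary endpoint in 6.2 is "Opioid utilization for the first 24 hours after surgery, including during surgery, calculated as oxycodone equivalent". The secondary endpoints are:
- pain scores, for example "Patient reported NRS scores in PACU and at 24 hours", with further scores on POD 1 and POD 3;
- "Reaction to surgical subpectoral incision";
- "Skin assessment of sensation in PACU (axilla, distal to surgical dressing".

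The Summary gives the same list, with VAS in place of NRS. Section 2.1 says the skin test records whether sensation is present or absent. The analysis text in 6.2 covers t, rank-sum, chi-square and Fisher tests. It contains no time-to-event method.

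**Data collected.** The Medication Usage Record logs the time, number of pills and a 0-10 pain score for each home dose. It also asks for one pain score 24 hours after the end of surgery. Neither pain item names a body site. PACU opioid use comes from the electronic record (2.1).

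**Opioid window.** The primary objective in 1.3 counts opioid "within the first 24 hours after surgery, including intraoperatively, as measured by oxycodone equivalents", which agrees with 6.2 and the Summary. The hypothesis in 1.2 refers to postoperative consumption only. Section 6.3 plans on 25 v 32 mg with SD 13 mg and does not say which window these describe.

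**The concern.** The site matters in this trial because the protocol itself describes two sources of pain. All participants have shoulder arthroscopy as well as the open tenodesis (3.1). The Background says the interscalene block, given in both arms, does not cover the area of the tenodesis incision. While that block works, an overall score in PACU probably reflects mainly the uncovered area. By 24 and 72 hours the block may have worn off, and an overall score may then combine shoulder and axillary pain. A total opioid dose cannot separate them either.

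Duration is stressed in three places, yet no time zero, event or analysis is defined for it. If the arms differ, the report could say that opioid use or overall pain differed. It would have no prespecified endpoint for saying that axillary pain was lower or that relief lasted longer. A sited score that is not asked for at the time cannot be recovered afterwards.

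**Working it through.** **1. Aim against endpoints**

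| Listed endpoint | Axillary pain score specified? | Duration? |
|---|---|---|
| Opioid to 24 h, including surgery | No, whole-patient dose | No, cumulative amount |
| NRS/VAS in PACU, at 24 h/POD 1 and on POD 3 | No site stated | No, separate time points |
| Reaction to incision | No, intraoperative signs | No |
| Axillary sensation in PACU | Axillary, but sensation and not pain | No, one time point |

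No row meets either element of Aim 1. The pain rows do give a coarse course of overall pain over three times.

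**2. The plan's own sample size**

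Inputs from 6.3: difference 32 − 25 = 7 mg, SD 13 mg, two-sided 0.05, power 0.90.

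Normal approximation: n = 2 × (1.960 + 1.282)² × 13² / 7² = 72.5, so 73 per group. The t-test calculation gives 73.45, so 74. The stated 72 is reproduced within two patients. Power by t test is 0.894 at 72 and 0.923 at 80. Nothing here disputes that figure.

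**3. What a duration endpoint could detect with 80 per arm**

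The candidate is time from end of surgery to first postoperative opioid. The documents do not give the share of the infiltration arm that takes an opioid within 24 hours, so 80%, 90% and 95% are assumed. Let S0 be the opioid-free share in that arm at 24 h, with proportional hazards, patients without opioid censored at 24 h, and no dropout.

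- Events = 80 × [(1 − S0) + (1 − S0^HR)]
- Power = Φ(|ln HR| × √events / 2 − 1.96)

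Example with S0 = 0.20 and HR = 0.75: 0.20^0.75 = 0.299. Events = 80 × (0.800 + 0.701) = 120.1. Then 0.2877 × √120.1 / 2 = 1.576, and Φ(1.576 − 1.96) = 0.35.

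| Infiltration arm taking opioid by 24 h (assumed) | HR for 80% power | Events at that HR | Power at HR 0.75 |
|---|---|---|---|
| 80% | 0.590 | 113 | 0.35 |
| 90% | 0.615 | 133 | 0.39 |
| 95% | 0.627 | 144 | 0.42 |

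The endpoint is feasible, but it is sensitive only to large effects.

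**4. Opioid window**

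The Summary, 1.3 and 6.2 agree that surgery is included. Section 1.2 does not include it. Section 6.1 omits it when naming the primary outcome, probably as shorthand. Section 6.3 is silent.

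If the planning values already describe the total, nothing changes. Suppose instead that they describe postoperative use only, and that intraoperative opioid adds independent variation of SD s with no difference between arms. Neither supposition is in the documents. The SD is then √(13² + s²), and power at 80 per arm falls from 0.923 to 0.91 (s = 3 mg), 0.885 (5), 0.82 (8) or 0.765 (10).

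**The case against.** The strongest reply is that the operational parts of the plan agree with each other. The hypothesis is about opioid use. The primary objective in 1.3 matches the primary endpoint, and the secondary objectives correspond to endpoints in 6.2. Opioid use is a reasonable measure of analgesic benefit. On this view only Aim 1, the Summary objective and one goal sentence are out of line, and rewording them is the cheaper repair. That stands: rewording would restore consistency, and it is offered below as the alternative. It would, however, give up the question that the Background sets out.

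Three stronger readings are tempting, and the documents do not support them.

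- *The trial will hold no axillary pain score at all.* The wording of the PACU and telephone NRS questions is not given, and the McGill form used in PACU is a figure not shown. What can be said is that no listed endpoint specifies the site and that the printed diary question names none.
- *Any statement about persistence of relief would be invented after the data are seen.* Overall scores in PACU, at 24 h and at 72 h are planned, and so is cumulative opioid to 24 h. They bear on persistence, coarsely. What is missing is a defined duration endpoint.
- *The difference in opioid window undermines the primary endpoint or the sample size.* Three places agree on the window, and 6.3 may already refer to the total. This is a wording conflict. The anesthesiologist and surgeon know the arm (2.1), which is a reason to show the two parts of the total, but it does not show that the total is wrong.

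**Conclusion.** The mismatch is real and worth correcting. Aim 1 and the Summary objective concern axillary pain and its duration, and 1.3 repeats the interest in duration, but the endpoint list specifies neither. The primary comparison of opioid use and its sample size are not called into question by this.

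How far overall scores at 24 and 72 hours blur an axillary difference is unknown, and the documents give nothing from which to estimate it. The power figures for time to first opioid rest on assumed opioid-use shares of 80 to 95%, proportional hazards and complete data. They show what the proposed endpoint could detect. They do not measure a loss under the present plan. The wording difference between 1.2 and 6.2 is minor and the point does not depend on it.

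**What to change.** **Preferred**

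1. At the existing PACU, 24 h and 72 h contacts, ask one NRS for the axilla or subpectoral incision separately from the shoulder. List it as a secondary endpoint.
2. Define one duration endpoint: time from end of surgery to first postoperative opioid, taken from PACU records and the timed diary. Confirm the first-dose time at the POD 1 call, censor patients with no opioid at a stated horizon, and analyse by Kaplan-Meier and log-rank. State that the measure is not site-specific and that 80 per arm detects only large effects.
3. Update the lists in the Summary, 1.3 and 6.2 together, so that no new inconsistency arises.

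**Alternative.** If the sponsor will not add these, reword Aim 1, the Summary objective and the goal sentence of 1.3 to 24-hour opioid use and overall pain. Make no claim about axillary pain or its duration.

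**Minor, in either case.** Keep the total as the primary endpoint and align 1.2 with it. State in 6.3 which window 25, 32 and 13 mg describe. Report intraoperative and postoperative opioid separately by arm as a descriptive breakdown, noting that the first may reflect dosing by staff who know the arm and the second may be shifted by carry-over.

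**Cost.** One extra question at three contacts, additional secondary endpoints, and a duration measure that depends on diary completeness. Section 15 lets the attachments change without a protocol amendment, but the edits to the Summary and to sections 1 and 6 are an amendment that needs IRB approval (10.2), and participant materials also go to the IRB.

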### TREATMENT PHASE:

Patients in both groups will receive an interscalene nerve block with 20 mL 0.5% bupivacaine. Subjects in the Pecs II block group will receive 20mL 0.25% bupivacaine; 20ml will be injected between pectoralis minor and serratus anterior muscles. The subpectoral surgical skin infiltration group will receive 15mL bupivacaine 0.25% by the surgeon. These medications will be obtained from the operating room omniceil. Neither the anesthesiologist nor surgeon will be blinded to the patient's group assignment, as they are the ones administering the treatment. All other stakeholders (patient, other caregivers, and research staff collecting the data) will be blinded to the patient's group assignment.

[figure not shown]

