### POST-OPERATIVE PHASE:

After initial recruitment, subjects' pain will be assessed via visual analog scale (VAS) by nursing staff during the post-operative period as per standard of care. The VAS pain scores are collected and documented in the patient's electronic medical record. Additionally, a standardized regimen of pain medication will be given to all subjects who are enrolled. The pain medications given to patients are standard of care medications and vary based on pain level. This is determined by the clinical staff caring for each patient. While the patient is in the PACU, an authorized research member will visit the patient and obtain a pain score using the Numeric Rating Scale (NRS) and McGill Pain Scale. Skin testing in the axilla will be done in PACU prior to discharge to evaluate the presence or absence of sensation in that area. Data on PACU opioid use documented in EPIC will be collected. On POD1 and POD 3, a phone call to the patient will be made to collect additional data on oxycodone use at home as well as an NRS score at 24 and 72 hours after surgery.

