## 6.4 Enrollment/Randomization/Masking Procedures

We will utilize randomization.com to generate a block randomization assignments for all 160 participants. Someone that is not a stakeholder in the study will make randomization envelopes, which include the study ID number, the treatment assignment, and dosage specifics. These randomization envelopes will then be distributed to the anesthesiologist pre-operatively by the authorized researcher after informed consent is obtained.

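### The primary total counts opioid given during surgery, when the anesthesiologist knows the arm and no dosing rule is stated; a postoperative-only comparison should be pre-specified

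*Combined protocol and SAP*

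**What the plan says.** The Protocol Summary, Section 1.3 and Section 6.2 agree that intraoperative opioid belongs to the primary outcome. Section 6.2 lists the primary endpoint as "Opioid utilization for the first 24 hours after surgery, including during surgery, calculated as oxycodone equivalent". Section 1.3 compares the arms on use "within the first 24 hours after surgery, including intraoperatively, as measured by oxycodone equivalents". The hypothesis in Section 1.2, by contrast, concerns postoperative consumption.

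On blinding, Section 2.1 (Treatment Phase) states: "Neither the anesthesiologist nor surgeon will be blinded to the patient's group assignment". It explains that these clinicians administer the treatments. The next sentence adds: "All other stakeholders (patient, other caregivers, and research staff collecting the data) will be blinded". Section 6.4 sends the allocation straight to the anesthesiologist: "These randomization envelopes will then be distributed to the anesthesiologist pre-operatively by the authorized researcher after informed consent is obtained".

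On opioid dosing, the only statement about standardization is in the Post-operative Phase paragraph of Section 2.1: "a standardized regimen of pain medication will be given to all subjects who are enrolled". The paragraph then says that the medications vary with pain level, and continues: "This is determined by the clinical staff caring for each patient". No regimen is written out. I found no rule for sedation or opioid during surgery; Section 1 only describes what is usual at the institution.

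Sections 6.1 and 6.2 contain no breakdown of the total by period and no postoperative-only analysis.

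**The concern.** For part of the primary outcome, the person who presumably decides the dose knows the arm, and the dose itself is the outcome. An anesthesiologist who expects the infiltration arm to be less well covered at the subpectoral incision could give opioid in anticipation. That would raise the control total without any difference in pain, and would favor Pecs II on the primary test.

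Section 6.1 refers to the patient being blinded. That helps where the patient asks for or reports the drug. It does not help during surgery, when the patient does neither. Because the endpoint is one sum, a significant result could come from analgesia, from dosing habits, or from both, and the planned analysis could not tell which.

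**Working it through.** **Inputs.** Section 6.3: means of 25 mg and 32 mg oxycodone-equivalent (difference 7 mg), common SD 13 mg, two-sided two-sample t test at 0.05, 72 per group for 90% power, 80 per arm enrolled. Attachment 15.1, first table (the one with an intravenous row): 10 mg IV morphine corresponds to 20 mg oral oxycodone, so 1 mg IV morphine = 2 mg oxycodone-equivalent. The size of any arm-related dosing shift is an assumption, because the documents give no intraoperative drug, dose or mean.

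**Step 1: the plan's own figure.** n per group = 2 × [13 × (1.960 + 1.282) / 7]² = 72.5, so 73 by the normal formula and 74 by the exact t calculation. Power at 72 per group is 0.894 (t test), and at 80 per group 0.923. The stated 72 is reproduced to within two patients, so the planning inputs can be used below.

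**Step 2: precision at the enrolled size.** SE = 13 × √(2/80) = 2.06 mg. With 158 degrees of freedom the critical value is 1.975, so an observed difference of about 1.975 × 2.06 = 4.06 mg is significant.

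**Step 3: effect of a shift b in the control arm when the true analgesic effect is zero.** The chance of a significant result favoring Pecs II is P(T > 1.975), where T is noncentral t with 158 degrees of freedom and noncentrality b/SE.

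| Assumed shift b (mg oxycodone-equivalent) | Same shift as mean IV morphine (mg) | Share of planned 7 mg | b/SE | Chance of significance favoring Pecs II |
|---|---|---|---|---|
| 0 | 0 | 0% | 0 | 2.5% |
| 1 | 0.5 | 14% | 0.49 | 7.0% |
| 2 | 1.0 | 29% | 0.97 | 16.0% |
| 3 | 1.5 | 43% | 1.46 | 30.5% |
| 4 | 2.0 | 57% | 1.95 | 49.0% |

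**Step 4: what a postoperative-only comparison does.** If the shift is confined to surgery and there is no true effect, the expected PACU-plus-home difference is zero. A test of that total therefore keeps its 2.5% error rate in favor of Pecs II for every b in the table.

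**Step 5: a weaker safeguard.** One could instead require only that the postoperative difference has the same sign as the total. I simulated this with SE 2.06 mg, no true effect and independent components. With intraoperative opioid contributing 10%, 25% or 50% of the variance (assumed), a 4 mg shift still gives a false claim in about 45%, 41% or 37% of trials, against 49% with no rule. Agreement in sign is not enough; the comparison needs its own estimate and test.

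**The case against.** Counting intraoperative opioid is defensible. Section 1 says the interscalene block does not cover the incision area, and extra opioid given because a patient reacts to that incision reflects a real analgesic difference. The unblinding is disclosed and, for the clinicians who perform the two techniques, hard to avoid. That the anesthesiologist controls intraoperative opioid is a natural inference, not something the documents state, and pre-emptive dosing is conjecture. The components could also be separated from data already planned. All of this stands. It is why the primary endpoint need not be replaced, but it does not supply a missing analysis.

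A reader might go further and infer that opioid dosing throughout the 24 hours can follow knowledge of the arm. The documents do not support that. Section 2.1 says other caregivers and the patient are blinded and ties postoperative medication to pain level, and home use is taken and logged by the blinded patient. The reference to clinical staff does not exclude the unblinded clinicians, but that is silence, not evidence.

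A reader might also infer that the standardized regimen is plainly contradicted. The sentences can equally describe a common set of medications given according to pain score. They are under-specified, and under blinded care the looseness would mainly add variability.

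**Conclusion.** The point holds for the intraoperative component. That component is inside the primary total, its dosing is presumably directed by someone who knows the arm, no arm-independent rule is stated, and no planned analysis isolates it. The postoperative component is better protected by the stated blinding.

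The documents show exposure to bias; they do not show that bias will occur or how large it would be. The 7%, 16% and 49% figures rest on assumed shifts of 1, 2 and 4 mg, a true effect of zero, the plan's SD of 13 mg, no dropout from 80 per arm, and a shift that acts only during surgery. This is an inexpensive improvement that protects how a positive result can be read. It is not a reason to regard the design as invalid.

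**What to change.** 1. In Section 6.2, report intraoperative, PACU and home opioid by arm, alongside the primary total.
2. Pre-specify the PACU-plus-home total over the first 24 hours as a key sensitivity analysis, with its own estimate, 95% confidence interval and test. This matches the postoperative hypothesis in Section 1.2.
3. State that if the primary total is significant but the postoperative comparison does not support it, the result will not be presented as a demonstrated reduction in postoperative opioid use.
4. Record the time and reason for each intraoperative opioid dose.
5. Reconcile the sentences in Section 2.1 (Post-operative Phase) on the standardized regimen and the discretion of clinical staff, and state that whatever the investigators choose applies identically in both arms. The choice of regimen is theirs, and no change to clinical workflow is asked for.

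The cost is one additional analysis, some wording and a few case report form fields. The outcome data are already planned: opioid use on the day of surgery (Section 4.2.2), PACU use from the medical record (Section 2.1), and home use from the follow-up calls (Section 4.2.3) and the medication usage record. The drawback is that a postoperative-only total omits any genuine benefit during surgery. For that reason it should be a sensitivity analysis and should not replace the primary endpoint.
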